10.7 Safety Analysis

10.7.1 Adverse Events

Adverse Events will be coded using the Medical Dictionary of Regulatory Activities (MedDRA version 23.0), the coded terms will be used for summarizing the AE(s). Adverse events will be analyzed using SAF population.

Incidence of AEs for user’s and other persons (if reported), will be presented in a separate table and listing.

An AE will be considered as treatment-emergent if the time of onset is on or after the time of the first study IMD administration or any event that exist prior to first dose and if it increased in severity during the study period. Handling of missing data and date are explained in section 9.5 (Imputation of missing data).

An overall summary table, which summarizes, the number and percentages of subjects with adverse events, serious adverse events, adverse events leading to death, adverse events related to IMD, adverse event related to procedure, action taken with study device, action taken to treat AE, associated to a device deficiency, subject withdrawn due to adverse event and adverse events by intensity categories, serious adverse device effects, unanticipated serious adverse device effect, will be provided for overall population.

AEs assessed with the relationship “unrelated” or “unlikely” will be classified as “not related” and AEs assessed with “possible”, “probable” or “definite” will be classified as “related”.

AEs Tables such as TEAE, SAE tables will be summarized by system organ class and preferred term. SOC will be sorted in descending order of counts.

A subject experiencing the same AE multiple times will be counted only once for that preferred term. Similarly, if a subject experiences multiple AEs within the same system organ class that subject will be counted only once in that system organ class. Maximum intensity will be considered if a subject has multiple severity reported for same AE. In summaries by relationship, if a subject has the same AE on multiple occasions, the closest relationship to study drug, will be used for summary.

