6.1.4 Discussion of clinical investigation design

This clinical investigation is undertaken to evaluate the effectiveness, safety and long term safety of Saypha® FILLER Lidocaine for lip augmentation and to assess the duration of the aesthetic effect after implantation.

The primary and one of the secondary performance endpoints (see section 6.1.1) is based on the 5-grade LFS (Lip Fullness Scale), a validated instrument for semi-quantitative assessment of lip fullness (see section 6.4.7). Difference of one grade on this scale is considered to be clinically meaningful since it can be visually recognized by various observers as demonstrated during validation of the scale.

In view of multicenter conduct of the investigation, the LFS assessment will be also evaluated centrally, by an experienced independent photographic reviewer (see section 6.4.7). This will allow for unified assessment of treatment responses across the sites and checking if any bias was introduced by inter-observer variability between the sites.

The clinical relevance of the investigation will be also supported by several secondary endpoints (see section 6.1.1), related to global aesthetic improvement (by using the GAIS) and subject's satisfaction with outcome (overall and the lips by using Face-QTM scales).

A randomization to IMD produced by one of the manufacturing sites 'HQ' and 'C1' will be done. It shall be shown that there is no difference in effectiveness and safety of the two IMDs between the two manufacturing sites.

Safety and long term safety of Saypha® FILLER Lidocaine for lip augmentation will be monitored by documentation of safety parameters (AEs and device deficiencies) (see section 6.4.13).

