7.1 Sample size

Confidence Interval calculation has been performed for the primary performance endpoint "The proportion of subjects ('responders') with the lip volume improved by ≥ 1 point versus baseline value at 6 weeks after initial treatment based on the investigator live assessment using a validated Lip Fullness Scale (LFS)". A responder is defined having at least ≥ 1 grade improvement compared to baseline values on the 5 point-validate lip fullness scale" (see section 6.1.1).

Approximately 110 subjects with moderate to severe volume deficiency of lips will be enrolled in order to obtain performance and safety data.

This sample size is arbitrarily selected and is considered sufficient to provide robust estimations on performance and safety parameters in the overall study population and in the subgroups regarding IMD manufacturing site. With a sample size of 100 a two-sided 95% confidence interval for a single proportion using the large sample normal approximation will extend by 0.059 in the overall population and 0.083 in the two manufacturing site subgroups from the observed proportion for an expected proportion of 0.900 (i.e., responder rate of 90%; calculated with nQuery Advanced 8.2.1.0). In order to cover subjects' drop-out or lost to follow-up the sample size will be increased by 10%. 110 subjects will be enrolled (with 55 subjects per manufacturing site). Thus, a robust estimation of the success rate at week 6 can be derived.

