7.3.2 Final analysis

Final analysis will be done after completion of the investigation by all subjects. All primary, secondary and safety endpoints will be tabulated by visit, if applicable, and summarized using descriptive statistics only. The final analysis will be done for the 'overall population' and for several defined subgroups (see section 7.3.10 for more information).

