7.3.10 Analysis of subgroups

Besides the 'overall population' (including all subjects enrolled in the investigation), which includes all enrolled subjects, the following subgroups will descriptively be analyzed:

IMD from manufacturing sites: 'HQ' and 'C1'

In this study, IMD from two different manufacturing sites ('C1' and 'HQ') will be used and subjects will be randomly assigned in a 1:1 ratio to 'IMD-C1' or 'IMD-HQ', respectively.

This subgroup analysis will compare both IMDs ('IMD-HQ' or 'IMD-C1') and separately analyze the results for the 'IMD-C1' and 'IMD-HQ' subgroups.

• Injection technique: 'retrograde technique' and 'bolus technique'

It is planned to descriptively analyze the performance of the IMD separated by injection technique.

The corresponding subgroup analysis will separately analyze the results for subjects treated with the two different injections techniques.

• Injection equipment: '27G ½" needle' versus cannula ('25G x 50mm cannula' or '22G x 70mm cannula')

It is planned to analyze the performance of the IMD separately for the injection equipment used (27G $\frac{1}{2}$ " needle versus cannula (25G x 50mm cannula or 22G x 70mm cannula)). Therefore it is planned to treat a minimum of 30 subjects either with needle or cannula (25G x 50mm cannula or 22G x 70mm cannula).

The corresponding subgroup analysis will separately analyze the results for subjects treated by means of the different injection equipment.

All subgroup analyses are planned to be performed for the primary performance endpoint and the main secondary performance endpoints.

The following secondary performance endpoints are planned to be analyzed:

- The percentage of responders, based on the investigator live assessment at 6, 12 and optional 18 months after the initial treatment using the validated LFS.
- The percentage of responders based on the independent photographic reviewer's assessments before initial treatment and at Week 6, Month 6, 12 and optional Month 18 after initial treatment, based on photographs and using the validated LFS.
- The percentage of subjects with an improvement relative to baseline photographs, (subjects who
 have been rated as "very much improved" or "much improved" or "improved"), based on the
 investigator assessment at Week 6, Month 6, 12 and optional Month 18 after initial treatment using
 the 5-point GAIS.
- The percentage of subjects with an improvement relative to baseline photographs (subjects who

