9.2 Analysis Population

Analysis Population	Definition
Safety Analysis Set (SAF)	The Safety Analysis Set (SAF) consists of all subjects who received at least one administration of the investigational medical device (IMD).
Full Analysis Set (FAS)	The Full Analysis Set (FAS) comprises all subjects who received at least one administration of the IMD and who had at least one post-treatment evaluation of the LFS.
Per-Protocol Set (PPS)	The Per-Protocol Set (PPS) includes all subjects of the FAS who have no major protocol deviations which affect the primary endpoint. Subjects with major protocol deviations which affect the primary endpoint will be excluded from the PPS.

	Statistical Analysis Plan	
	Sponsor: CROMA-PHARMA GmbH	
	Study Number: CPH-101-201479	Version: Final 1.0 Date: 07 Jun 2021

For this purpose, protocol deviations that could interfere with the objectives of the study, use of prohibited concomitant medications/procedures or deviation of the inclusion/exclusion criteria etc. will be assessed as ‘minor’ or ‘major’ in collaboration with the sponsor in the Data Review Meeting (DRM). The criteria for this assessment will be defined before analysis in the SAP. Listings will be prepared to assess the eligibility of all subjects during the DRM.

All safety analyses will be based on the SAF. The primary data set for effectiveness analysis will be the FAS and PPS.

Subjects who have been administered wrong IMD which is different from randomized will be analyzed as randomized (Planned) for FAS and will be analyzed under IMD, which was administered at first, for SAF. These subjects will not be included in PPS.

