10.7.2 Device Deficiencies

The following will be assessed for the device deficiency:

- Nature of Device Deficiency:
- Is an individual affected by the Device Deficiency?
- Relatedness of Device Deficiency to an (S)AE
- Action Taken with the device

	Statistical Analysis Plan Sponsor: CROMA-PHARMA GmbH	
	Study Number: CPH-101-201479	Version: Final 1.0 Date: 07 Jun 2021

Device deficiency related items will be summarized by number and percentage using SAF population. Listings will be provided for Device Deficiency.

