10.8 Subgroup Analyses

Besides the ‘overall population’ (including all subjects enrolled in the investigation), which includes all enrolled subjects, the following subgroups will descriptively be analyzed:

- **IMD from manufacturing sites: ‘HQ’ and ‘C1’**
 IMD from two different manufacturing sites (‘C1’ and ‘HQ’) will be used and subjects will be randomly assigned in a 1:1 ratio to ‘IMD-C1’ or ‘IMD-HQ’, respectively.
 Subgroup analysis will compare both IMDs (‘IMD-HQ’ or ‘IMD-C1’) and separately analyze the results for the ‘IMD-C1’ and ‘IMD-HQ’ subgroups.
 Summary of subgroup analysis will compare both IMDs (‘IMD-HQ’ or ‘IMD-C1’) will be analyzed descriptively using FAS populations
- **Injection technique: ‘retrograde technique’ and ‘bolus technique’**
 Subgroup analysis will separately analyze the results for subjects treated with the two different injections techniques.
 Summary of different injections techniques will be analyzed descriptively using FAS populations
- **Injection equipment: ‘27G ½” needle’ versus cannula (‘25G x 50mm cannula’ or ‘22G x 70mm cannula’)**
 Subgroup analysis will separately analyze the results for subjects treated by means of the different injection equipment.
 All subgroup analyses are planned to be performed for the primary performance endpoint and the main secondary performance endpoints.

All subgroup analyses are planned to be performed for the primary performance endpoint and the main secondary performance endpoints using FAS population only.

The following secondary performance endpoints are planned to be analyzed:

- The percentage of responders, based on the investigator live assessment at 6, 12 and optional 18 months after the initial treatment using the validated LFS.

- The percentage of responders based on the independent photographic reviewer’s assessments before initial treatment and at Week 6, Month 6, 12 and optional Month 18 after initial treatment, based on photographs and using the validated LFS.
- The percentage of subjects with an improvement relative to baseline photographs, (subjects who have been rated as “very much improved” or “much improved” or “improved”), based on the investigator assessment at Week 6, Month 6, 12 and optional Month 18 after initial treatment using the 5-point GAIS.

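### The plan states a safety aim for HQ versus C1 product but specifies no adverse event or device-deficiency table by manufacturing site

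*SAP*

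**What the plan says.** Passages that point to safety by manufacturing site:

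- Protocol 6.1.4, on the purpose of the randomisation: "It shall be shown that there is no difference in effectiveness and safety of the two IMDs between the two manufacturing sites".
- Protocol 7.1 calls the sample size sufficient for robust estimation of "performance and safety parameters in the overall study population and in the subgroups regarding IMD manufacturing site". SAP 9.6 repeats this, and protocol 3.3 and SAP 8.1.2 say much the same.
- SAP 9.2 rules that a subject given the wrong product "will be analyzed under IMD, which was administered at first, for SAF".

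Passages that define the safety output:

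- SAP 10.7.1: the adverse event overview closes with "unanticipated serious adverse device effect, will be provided for overall population". The tables by system organ class and preferred term carry no statement on grouping.
- SAP 10.7.2: "Device deficiency related items will be summarized by number and percentage using SAF population". Again no grouping is stated.
- SAP 10.8: "All subgroup analyses are planned to be performed for the primary performance endpoint and the main secondary performance endpoints using FAS population only". Protocol 7.3.10 has the same limit to performance endpoints, without the restriction to the FAS.
- Protocol 7.3.8 summarises safety for all dosed subjects and mentions no split.

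**The concern.** The plan raises a safety question about the two products, randomises subjects in a way that could inform it, and then specifies no table that shows it.

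The question has substance. Protocol 2.2 reports that process parameters were adapted during the transfer, that most production equipment is new, and that HQ material is not CE-certified. Protocol 4.5 nevertheless takes the new site to have no effect on safety. This study can examine that assumption in concurrent randomised groups. If the tables are pooled, a reader could find an HQ/C1 imbalance in adverse events only by counting from the subject listings, and the per-site safety estimates claimed in the sample-size text would appear nowhere.

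**Working it through.** **1. The text, side by side**

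| Question | What the plan gives |
|---|---|
| Is safety by site an aim? | Yes in protocol 6.1.4. The listed additional objective (protocol 5.1, SAP 7.1.2) names effectiveness only. |
| Is per-site safety precision claimed? | Yes: protocol 3.3 and 7.1, SAP 8.1.2 and 9.6. |
| Is there a rule for assigning SAF subjects to a product? | Yes, SAP 9.2. It has an effect only where SAF output is split by product. |
| Is the adverse event overview by site? | No; overall population (SAP 10.7.1). |
| Are SOC/PT and device-deficiency tables by site? | Not stated (SAP 10.7.1, 10.7.2). |
| Does the subgroup section add safety? | No; primary and five listed secondary performance endpoints, FAS only (SAP 10.8). |
| Does SAP section 11 record a change? | No. |

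**2. The plan's own precision figures**

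Half-width = 1.96 × √(p(1−p)/n), with p = 0.900:

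- n = 100: 1.96 × √(0.09/100) = 0.059
- n = 50: 1.96 × √(0.09/50) = 0.083

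Both match protocol 7.1 and SAP 9.6. They concern the lip fullness responder rate. No safety rate or safety interval is given.

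**3. Assumed safety rates**

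The documents give no adverse event rate for lips. I take a range from the sponsor's two earlier studies:

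- 9.4% of subjects with an adverse device effect (FLASH 1: other indications, product without lidocaine; protocol 4.2.1)
- 43.3% (FINO: nasolabial folds, events rated procedure-related; protocol 4.2.2)

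**4. What pooling hides**

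The middle of the range is (9.4 + 43.3)/2 = 26.4%, about 29 of 110 subjects. The same pooled row fits both of these splits:

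- 15/55 versus 14/55: 27.3% versus 25.5%, gap 1.8 points
- 20/55 versus 9/55: 36.4% versus 16.4%, gap 20.0 points

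**5. What a by-site table could show**

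Per group: 1.96 × √(p(1−p)/55). Difference at equal rates: 1.96 × √(2p(1−p)/n).

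| Rate p | Per group, n = 55 | Difference, 55 per group | Difference, 50 per group |
|---|---|---|---|
| 0.094 | 0.077 | 0.109 | 0.114 |
| 0.433 | 0.131 | 0.185 | 0.194 |

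For an event not seen at all, the two-sided 95% upper bound is 1 − 0.025^(1/n):

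- 55 HQ subjects: 1 − 0.025^(1/55) = 6.5%
- pooled 110: 1 − 0.025^(1/110) = 3.3%

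The pooled bound applies to HQ product only if the two products are already taken to be equally safe.

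**The case against.** The strongest reply is that safety by site was intended and the SAP is merely untidy. SAP 9.8 says that safety endpoints will be tabulated and that the final analysis covers the overall population and defined subgroups. The SAP 9.2 assignment rule makes sense only with SAF output by product. This shows a likely intention but specifies no table. The protocol text behind SAP 9.8 (section 7.3.2) refers the subgroups to 7.3.10, which is limited to performance endpoints, and the specific section, SAP 10.8, restricts by-site work to the FAS.

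Second, the mandate is modest. The listed HQ/C1 objective concerns effectiveness, protocol 5.2 calls the study non-comparative, and the safety aim is one sentence in a design discussion plus general sample-size wording. That stands, and it is why the gap is a missing descriptive summary and not a missing test. Protocol 5.2 does not bar such a summary, since effectiveness is already to be described by site.

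Third, pain on the NPRS is among the endpoints analysed by site, and pain graded 4 or more is recorded as an adverse event (protocol 6.4.8). One tolerability outcome is therefore covered, although as a performance endpoint on the FAS. Swelling, haematoma, nodules, serious events and device deficiencies are not.

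Fourth, the groups are small and the 29/110 splits are hypothetical. Both points are true. The splits illustrate what a pooled row cannot reveal; they do not predict a result.

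**Conclusion.** The concern holds. Followed as written, the plan produces no specified adverse event or device-deficiency summary by manufacturing site, although protocol 6.1.4 states a safety aim for that contrast and the sample-size text claims per-site safety estimates. This conclusion rests on the text and does not depend on any assumed rate.

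The figures in the working do rest on the assumed range of 9.4% to 43.3% and on 55 subjects per group. On that basis each group's rate would be known to within 7.7 to 13.1 points and the HQ−C1 difference to within 10.9 to 18.5 points. A by-site table is worth having as description, but it cannot deliver the demonstration that protocol 6.1.4 asks for, and the SAP should say so.

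**What to change.** For the final analysis:

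- Present the adverse event overview and the SOC/PT, related-event, SAE, SADE and device-deficiency tables in the SAF with columns IMD-HQ, IMD-C1 and Total, assigning subjects by the product first administered, as SAP 9.2 already provides.
- Add safety (SAF) to the manufacturing-site entry in SAP 10.8.
- Record the addition in SAP section 11. State there that the comparison is descriptive and, in line with protocol 5.2, cannot demonstrate absence of a difference. If the change is made after the interim analysis, say that too.
- Risk differences with 95% confidence intervals are optional.

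The interim analysis can stay on the overall population as planned.

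The cost is a SAP update before the final database lock: two extra columns in tables already planned, one entry in 10.8 and one row in section 11. No new data, visits or subjects are needed. Protocol 7.7 requires a protocol amendment only where the effectiveness analysis is affected, and here it is not. Rewording protocol 6.1.4 would need a written amendment (protocol section 9); it can wait for the next one, since the table change does not depend on it.

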10.7.2 Device Deficiencies

The following will be assessed for the device deficiency:

- Nature of Device Deficiency:
- Is an individual affected by the Device Deficiency?
- Relatedness of Device Deficiency to an (S)AE
- Action Taken with the device

	Statistical Analysis Plan Sponsor: CROMA-PHARMA GmbH	
	Study Number: CPH-101-201479	Version: Final 1.0 Date: 07 Jun 2021

Device deficiency related items will be summarized by number and percentage using SAF population. Listings will be provided for Device Deficiency.

10.7.3 Urine pregnancy test

Listing will be provided for the Urine pregnancy test.

10.7.4 Multicenter trial

This study will take place in up to three investigation sites, however, due to the limited number of subjects no site stratification is planned

10.8 Subgroup Analyses

Besides the ‘overall population’ (including all subjects enrolled in the investigation), which includes all enrolled subjects, the following subgroups will descriptively be analyzed:

- **IMD from manufacturing sites: ‘HQ’ and ‘C1’**
 IMD from two different manufacturing sites (‘C1’ and ‘HQ’) will be used and subjects will be randomly assigned in a 1:1 ratio to ‘IMD-C1’ or ‘IMD-HQ’, respectively.
 Subgroup analysis will compare both IMDs (‘IMD-HQ’ or ‘IMD-C1’) and separately analyze the results for the ‘IMD-C1’ and ‘IMD-HQ’ subgroups.
 Summary of subgroup analysis will compare both IMDs (‘IMD-HQ’ or ‘IMD-C1’) will be analyzed descriptively using FAS populations
- **Injection technique: ‘retrograde technique’ and ‘bolus technique’**
 Subgroup analysis will separately analyze the results for subjects treated with the two different injections techniques.
 Summary of different injections techniques will be analyzed descriptively using FAS populations
- **Injection equipment: ‘27G ½” needle’ versus cannula (‘25G x 50mm cannula’ or ‘22G x 70mm cannula’)**
 Subgroup analysis will separately analyze the results for subjects treated by means of the different injection equipment.
 All subgroup analyses are planned to be performed for the primary performance endpoint and the main secondary performance endpoints.

All subgroup analyses are planned to be performed for the primary performance endpoint and the main secondary performance endpoints using FAS population only.

The following secondary performance endpoints are planned to be analyzed:

- The percentage of responders, based on the investigator live assessment at 6, 12 and optional 18 months after the initial treatment using the validated LFS.

- The percentage of responders based on the independent photographic reviewer’s assessments before initial treatment and at Week 6, Month 6, 12 and optional Month 18 after initial treatment, based on photographs and using the validated LFS.
- The percentage of subjects with an improvement relative to baseline photographs, (subjects who have been rated as “very much improved” or “much improved” or “improved”), based on the investigator assessment at Week 6, Month 6, 12 and optional Month 18 after initial treatment using the 5-point GAIS.
- The percentage of subjects with an improvement relative to baseline photographs (subjects who have been rated as “very much improved” or “much improved” or “improved”), based on subject assessment at Week 6, Month 6, 12 and optional Month 18 after initial treatment, using the 5-point GAIS.
- Subject’s perception of pain after initial and touch-up treatment with Saypha® FILLER Lidocaine using the 11-point Numeric Pain Rating Scale (NPRS), where 0 is no pain and 10 is the worst pain imaginable.

